4.2 Exclusion Criteria

- 4.2.1 Children (< 18 years) are excluded because pancreatic and periampullary tumors rarely occur in this age group. Furthermore, treatment requires a great deal of patient cooperation including the ability to lie still for several hours in an isolated room.
- 4.2.2 Uncontrolled intercurrent illness including, but not limited to, ongoing or active infection (or infections requiring systemic antibiotic treatment), symptomatic congestive heart failure, unstable angina pectoris, cardiac arrhythmia, or psychiatric illness/social situations that would limit compliance with study requirements.
- 4.2.3 Any concurrent malignancy other than non-melanoma skin cancer, non-invasive bladder cancer, early stage prostate cancer, or carcinoma in situ of the cervix. Patients with a previous non-pancreatic, non-periampullary malignancy without evidence of disease for > 5 years will be allowed to enter the trial.
- 4.2.4 Pregnant and breastfeeding women are excluded as are women of child-bearing potential who are unwilling or unable to use an acceptable method of birth control (hormonal or barrier method of birth control; abstinence) to avoid pregnancy for the duration of the study. Should a woman become pregnant or suspect she is pregnant while participating in this study, she should inform her treating physician immediately.
- 4.2.5 Women who are not post-menopausal (as defined in Appendix III) and have a positive urine or serum pregnancy test or refuse to take a pregnancy test.
- 4.2.6 Patients with a life expectancy of < 3 months.
- 4.2.7 Patients with metastatic disease.

5. REGISTRATION PROCEDURES

5.1 General Guidelines

Subjects will be identified per the recommendation of surgeons or GI Combined Modality Tumor Board or equivalent combined modality assessment. Subjects will be recruited through self-referral and the advice of their attending physician. No advertisement will be used to recruit subjects.

5.2 **Registration Process**

A member of the research team (most likely the research coordinator or research nurse) will enroll the patient into the trial. Subjects will be entered into the patient database at Johns Hopkins Hospital. Consent will be obtained after a clear and thorough discussion between the patient and the principal investigator or any of the co-investigators in clinic. Any patients that are deemed by the principal investigator or co-investigators to be mentally or physically incapable of consent will not be included in the study.

6. SBRT ADMINISTRATION AND RADIATION TREATMENT PLANNING

6.1 Pre-Linac based SBRT Tests, Procedures, and Planning

The following will be completed prior to Linac based SBRT:

- a. Medical history and clinical examination.
- b. CBC with differential, Chemistry Panel, CA19-9.
- c. Gold fiducial seed placement percutaneously, intraoperatively, or under endoscopic ultrasound guidance, which may be performed prior to enrollment.
- d. Pathologic confirmation of malignancy. (Core biopsies during gold fiducial placement as needed or optional).
- e. CT Pancreas or C/A/P scan required; FDG-PET or FDG-PET/CT (dual phase) recommended at the discretion of the treating physician.
- f. Signed informed consent document.
- g. Baseline collection of EORTC QLQ C-30/ PAN26 QOL.
- h. Optional whole body dynamic PET/CT
- 6.1.1 Fiducials

Treatment on this protocol requires placement of 1-5 gold (99.9% pure, 1-5 mm length, or visicoils) fiducials for targeting purposes. The fiducials will be used as surrogates for targeting the daily tumor position during treatment. The fiducials will be placed directly into the tumor and/or periphery under endoscopic ultrasound or CT guidance. When possible, clips or fiducials will also be placed in the proximal duodenum directly adjacent to the pancreatic tumor. Fiducials may be implanted prior to enrollment as this is an acceptable standard of care procedure for any patient receiving radiotherapy for locally advanced pancreatic or periampullary cancer. Also, if a patient had an attempted surgical resection that was aborted, fiducials may have been implanted intraoperatively, which is also allowable prior to study enrollment.

If fiducials are not placed intraoperatively and/or prior to enrollment, placement will be done and is expected to be done on an outpatient basis. In rare occurrences when fiducials/clips cannot be placed, patients may be treated at the discretion of the PI.

6.1.2 Simulation

- 1) Simulation should be done following placement of fiducials; however, this may vary and is at the discretion of the principal investigator.
- 2) Typically, patients will be positioned supine in an Alpha Cradle or equivalent immobilization device that will be custom-made for each patient.
- 3) Standard free-breathing CT and respiratory-correlated 4-D pancreatic protocol CT will be obtained on each patient. The 4D-CT scan will be used for characterizing target motion during quiet respiration. For more accurate tumor delineation, an arterial phase pancreatic protocol CT may be obtained (typically during expiration breath hold, 1.25 mm slices). Fiducial to fiducial fusions between these scans should be utilized whenever possible. The simulation scan should include T4/T5 to L5/S1 (upper abdomen).
- 4) A research dMRI may be conducted at the time of simulation. In order to derive a set of 4D anatomic images that are directly comparable to 4D-CT, the Department of Radiation Oncology has developed a retrospective, slicestacking, sorting technique that relies on a respiratory trace collected simultaneously with multi-slice 2D dMRI sequences (bSSFP and HASTE). The final rendered "4D-MRI," or set of phase-binned 3D-MR volumes, represents a statistically-averaged breathing cycle over the long-duration imaging session. Because this frame-averaging approach can result in image blurring in the context of breathing variability, secondary anatomic-based sorting methods are employed to improve on image quality (contrast). Further,

for each imaged slice location and breathing phase bin a sufficiently large number of samples permits derivation of meaningful, image-based strategies to convey variability information, such as via rendering a corresponding "4D-MRI standard deviation" image. This method is independent of the imaging sequence employed and is generically suitable for multiple sites of disease.

- 5) IV and oral contrast must be used for simulation, unless the patient has an allergy that cannot be adequately premedicated. In these situations, the plan should be fused with an IV contrast CT scan or MRI (ideally in a similar treatment position).
- 6) Motion management can be addressed using respiratory gating, breath-hold, respiratory tracking, or abdominal compression. Specialized compression belts may be utilized for some patients. They come in 4 sizes: S, M, L, and XL. Each belt has an adjustable pressure cuff which can be used to reduce breathing motion. Fluoroscopy is used to assess motion of implanted gold markers before and after compression. The goal is to reduce motion from typically 11-22 mm peak to less than 5 mm. If the fiducial motion cannot be decreased to 5 mm or less, then respiratory gating using either the Varian Respiratory Management (RPM) system or the Elekta Active Breathing Coordinator (ABC) will be utilized for treatment delivery. Prior to simulation, standard guidelines will be followed.
- 7) As long as the specified dosimetric parameters for SBRT are reached, patients may be treated on any IGRT-enabled machine.
- 8) All patients must start Linac based SBRT within 4 weeks of the simulation scan.
- 6.1.3 Treatment Planning
 - 1) When available, an FDG-PET scan is preferred for treatment planning purposes and will be acquired on a flat table top with the same immobilization devices used for the treatment planning CT simulation.
 - An SBRT treatment plan will be developed using Pinnaclebased on tumor geometry and location. Institutional standards for radiation quality assurance and radiation delivery will be utilized.
 - 3) The tumor volume (GTV), as identified on the treatment planning CT, will be contoured by an attending physician from Johns Hopkins Hospital. The final GTV will be defined by the attending radiation oncologist after reviewing the diagnostic CT, respiratory-correlated 4D-CT scan, pancreas protocol CT, and/or the FDG-PET/CT scan. These scans will be used to define the ITV (internal target volume). The final PTV (planning treatment volume) expansion will consist of an additional 2-3mm of margin expansion, except if the margin results in expansion into the duodenum or stomach. In these cases, margin expansion is allowed to be non-uniform. The dose will be prescribed to the isodose line that completely surrounds the PTV. It is recommended that 6-12 co-planar fields be used in the radiation treatment plan.
 - 4) Contours of the fiducials used for target localization will be generated on the applicable image sets, to be used for patient setup on treatment.
 - 5) Radiation dose to the adjacent normal tissue will be minimized. Based on an analysis of duodenal toxicity representing pooled data from 3 previous prospective studies, the following dose constraints must be met: V15<9cc, V20<3cc. The duodenum (duo@PTV) as defined for these dosing parameters includes the entire duodenum on the same axial plane as the PTV and duodenum 1 cm above and 1 cm below the PTV. In patients who have

undergone pancreaticoduodenectomy, the regions of the pancreaticojejunostomy, gastrojejunostomy, and hepaticojejunostomy that lie 1 cm above or below or lateral to the PTV will also be delineated as structures of interest. V15 and V20 are defined as the percent volume receiving 15 Gy and 20 Gy, respectively. No more than 1cc of the proximal duodenum or proximal stomach may exceed 33 Gy for cohort B (25 Gy for cohort A, re-irradiation patients). The remainder of the normal tissues will be limited as follows:

- Liver (excluding tumor): 50% should be limited to <12 Gy (<8 Gy for cohort A-re-irradiation patients)
- Kidney: Combined volume for both should have 75% <12 Gy (<8 Gy for cohort A-re-irradiation patients)
- Stomach and duodenum: V15<9cc (V12<9 cc for cohort A) and V20<3cc (V15<3 cc for cohort A). 50% should be limited to <12 Gy (<8 Gy for cohort A) (no more than 1 cc of proximal stomach can receive >33 Gy for cohort B, (no more than 1 cc of proximal stomach can receive >25 Gy for cohort A, re-irradiation patients)
- Spinal Cord: no more than 1cc can receive >8 Gy (>6 Gy for cohort A).
- 6) No more than 1cc of the PTV can receive >130% of the prescription dose (4290cGy for 6.6Gy x 5; 3250cGy for 5Gyx5, cohort A).
- 7) Greater than 90% of the PTV should receive 100% of the prescription dose (3300cGy for 6.6Gy x 5; 2500cGy for 5Gyx5).
- 8) If above constraints cannot be achieved, then 100% of the GTV must receive at least 25 Gy (20 Gy for cohort A) (an allowed minor deviation, which will be documented).

If this constraint cannot be met, the patient should be removed from the protocol.

6.1.4 Linac based SBRT Treatment Delivery

Patients will receive 5 fractions of 5 Gy or 6.6 Gy delivered over a five-day period, as delineated above, based on whether or not they have received prior radiation therapy to the pancreatic region. Ideally all 5 fractions should be delivered Monday through Friday; however, treatment may be delivered over 2 weeks, as long as the patient receives at least 2 fractions per week.

Treatment Delivery (LINAC-based):

- 1) Initial patient positioning will be based on volumetric kV (cone-beam CT) imaging with shifts to bony anatomy as appropriate.
- 2) Orthogonal kV/MV or kV/kV projection imaging will be used to verify the location of the fiducials prior to delivery of first treatment beam. A secondary shift based on the location of fiducials may be utilized, as indicated by the position of the fiducials. For free-breathing treatments, kV fluoroscopic images should be obtained to confirm the anticipated position of these fiducials during the entire respiratory cycle.
- Active monitoring of treatment delivery accuracy will be accomplished using kV and/or MV projection imaging, either immediately before or during all (or a subset of) treatment fields.

- 4) Patient-specific dosimetric quality assurance (QA) will be performed as per standard practice in the Department of Radiation Oncology and Molecular Radiation Sciences at Johns Hopkins Hospital.
- 6.1.5 Post-Linac based SBRT Follow-Up Following Linac based SBRT, all patients will be monitored clinically and with serial imaging (CT scans and/or PET/CT if possible and as deemed necessary by the treating physician).

A detailed medical history with physical examination and quality of life assessment will be performed at 4-6 weeks, 4 months, 6 months, 9 months and 1 year after radiation treatment.

In years 2-5, the follow up interval will be every 3-6 months, as determined by the principal investigator. Follow up intervals may also be more frequent as indicated clinically. A complete blood count (CBC) with differential, comprehensive chemistry panel, tumor marker studies, and quality of life assessment will be performed at each follow-up interval.

6.2 General Concomitant Medication and Supportive Care Guidelines

6.2.1 Antidiarrheals and Anti-emetics

For symptoms of diarrhea and/or abdominal cramping, patients will be instructed to take anti-diarrheals. Additional antidiarrheal measures may be used at the discretion of the treating physician. Patients should be instructed to increase fluid intake to help maintain fluid and electrolyte balance during episodes of diarrhea.

For symptoms of nausea and vomiting, anti-emics will be given one hour prior to Linac based SBRT and for up to 5 days following Linac basedSBRT on an as-needed basis. Additionally, patients will be instructed to increase fluid intake.

All patients will be prescribed proton pump inhibitors (PPIs), which should begin by the start of Linac based SBRT and continue for a minimum of 6 months following Linac based SBRT.

6.2.2 Other Concomitant Medications

Therapies considered necessary for the patient's well being may be given at the discretion of the investigator. Other concomitant medications should be avoided except for analgesics, chronic treatments for concomitant medical conditions, or agents required for life-threatening medical problems. Specifically, if the patient is being treated with chemotherapy, it is recommended that chemotherapy be discontinued at least one week prior to initiation of Linac based SBRT and that resumption of chemotherapy be delayed for at least one week following the conclusion of Linac based SBRT. In general, prescription of these medications will be presided over by the patient's attending medical oncologist.

6.2.3 Supportive Care Guidelines

All commonly accepted supportive care guidelines will be used.

6.2.4 Use of Radioisotopes/Rad Machines Stereotactic radiotherapy will be performed using Linac based radiation machines. The radiation treatment plan will be designed to use multiple beams of radiation to concentrate large doses of radiation within a tumor. The Linac machines are equipped with cone beam CT imaging that can be used to deliver image-guided radiation therapy (IGRT). IGRT allows delivery of highly accurate, stereotactic radiation treatment. The use of cone beam CT images during IGRT is considered standard of care treatment.

Uncertainties in tumor location are minimized because these machines have onboard, volumetric imaging for accuracy in initial patient setup; kV and MV projection imaging during treatment is used to monitor delivery accuracy and/or make corrections to the patients' position. The radioactive tracer FDG will be used to perform PET scans (when available), a special imaging procedure. Positron emission tomography (PET) is a type of nuclear medicine examination, which is based on the administration of a small amount of a radioactive FDG agent. The tracer (FDG) is a modified form of glucose, a sugar normally found in the bloodstream and used by cells in the body for energy. FDG is eliminated in the urine. With special imaging equipment, it is possible to detect radiation from the administered radioactive agent and obtain images of the body.

6.2.5 Risk Information

It is difficult at this time to predict with confidence the percentage rate of complications from the proposed Linac based SBRT treatment. However, it is reasonable to extrapolate from the current experience with radiotherapy in and around the pancreas. Based upon prior phase I and phase II studies, we anticipate that the toxicities associated with this treatment will be acceptable.

Toxicities commonly associated with such treatment include nausea, vomiting, fatigue, anorexia and weight loss. Severe side effects such as gastrointestinal (GI) obstruction, perforation, or hemorrhage are uncommon complications, occurring in <5% of patients undergoing standard radiation therapy for pancreatic cancer. Although we expect a comparable rate of complications with fractionated Linac based SBRT, it is important to note that vomiting, GI obstruction, GI hemorrhage, anorexia and weight loss are also commonly associated with pancreatic cancer progression. Clinical and radiographic assessments will be performed in an effort to identify these effects, ascertain their etiology and provide the most appropriate palliative measures. Hepatic and renal toxicity is not anticipated given the expectation of limited incidental irradiation of these organs. Complications, if any, will be graded according to the CTCAE, National Cancer Institute, version 4.0. We will also utilize the RTOG scale for grading acute and chronic radiotherapy toxicities.

6.3 **Duration of Study**

It is anticipated that this study will last approximately 42 months (30 months of accrual and 12 months while cohort matures).

6.4 **Duration of Follow Up**

We estimate that most patients will remain a subject in this study for approximately one year Patients will remain enrolled on this protocol for a maximum of 5 years or until patient withdrawal. One year after Linac based SBRT, patients should undergo standard follow-up every 3-6 months, as determined by the treating physician. Patients that have completed the 5 year follow-up will continue being followed for survival information until death. The administration of subsequent chemotherapy and/or other antineoplastic treatment following Linac based SBRT will be at the discretion of each patient's attending medical oncologist. If participants become very ill and cannot travel to JHH for follow-up appointments, the study team will mail Quality of Life Questionnaires and requisition medical records from local providers. This is expected due to progression profile. If all protocol parameters are met this will not constitute a protocol deviation.

6.5 Criteria for Removal from Study

Patients will be removed from the study for any of the following reasons: death or patient withdrawal. The protocol director may also withdraw a patient from the study for one or more of the following reasons: failure of the patient to follow the instructions of the protocol study staff, the protocol director decides that continuing participation could be harmful to the patient, pregnancy (if applicable), the patient needs treatment not allowed in the study, the study is cancelled, other administrative reasons, or unanticipated circumstances. Patients that have been removed from or discontinue the study will be followed for survival information until death.

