The sample size is 60 patients per cohort. The primary outcome used to determine the sample size is the percentage of individuals with a late gastrointestinal toxicity (grade 2-4) at one year. The late grade 2 or greater toxicity rates was previously observed for other treatment regiments for locally advanced pancreatic cancer were approximately 40%. We hypothesize that in each cohort, the toxicity rate for this regimen will be 20%, a 50% reduction. The stopping rules for futility were calculated based upon a two-stage design with a total sample size of 60 and an interim analysis of 16 patients (note: accrual will continue while interim analysis is being conducted). Within 16 patients, if 7 or more patients have late grade 2 or greater gastritis, enteritis, fistula, ulcer, or late grade 3 or greater GI toxicity, the trial will be stopped. If 6 or fewer patients have late grade 2 or greater gastritis, enteritis, fistula, ulcer, or late grade 3 or greater GI toxicity, then the study will continue enrolling patients until 60 patients have been accrued. After 60 patients are enrolled, if 17 or more of the patients have late grade 2 or greater gastritis, enteritis, fistula, ulcer, or late grade 3 or greater GI toxicity, the null hypothesis will not be rejected. If 16 or fewer of the patients have late grade 2 or greater gastritis, enteritis, fistula, ulcer, or late grade 3 or greater GI toxicity, we will conclude that one year late toxicity is below 40%. This design will reach 91% power with 2% type I error for grade 2 or greater late toxicity, and the probability of early termination is 0.47. In addition, this sample size will reach 89% and 90% power to test the increase of 1-year local progression free survival from 30% to 45% in cohort A and 50% to 65% in cohort B, respectively.

The calculation is based on a one-sided test at significance level 0.04, assuming exponential distribution for local progression time and 2.5 year uniform accrual time with 1 year follow up.

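### Section 6.5 names only survival follow-up after removal from the study, so late GI toxicity in some treated patients may go uncollected during the primary risk window

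*Combined protocol and SAP*

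**What the plan says.** Section 6.5 removes patients for death or their own withdrawal. It then adds discretion: "The protocol director may also withdraw a patient from the study for one or more of the following reasons". The listed reasons include not following staff instructions, needing treatment outside the protocol, administrative or unforeseen circumstances, and that "the protocol director decides that continuing participation could be harmful to the patient". The section closes: "Patients that have been removed from or discontinue the study will be followed for survival information until death".

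Two routes collect information from patients who cannot attend. Section 6.4 provides that, for participants too ill to travel, "the study team will mail Quality of Life Questionnaires and requisition medical records from local providers". Footnote 13 of the study calendar (section 10) allows toxicity evaluation by telephone when a participant cannot come back. Neither mentions patients already removed.

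Section 13.4.2 sizes each cohort on "the percentage of individuals with a late gastrointestinal toxicity (grade 2-4) at one year". It states "The sample size is 60 patients per cohort" and hypothesises that "the toxicity rate for this regimen will be 20%, a 50% reduction", against about 40% with earlier regimens. The trial stops if 7 or more of the first 16 patients have an event. If it continues, 16 or fewer events after 60 are enrolled leads to the conclusion that one-year late toxicity is below 40%. Section 13.2 defines a population for efficacy only.

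**The concern.** The protocol treatment is complete before the primary endpoint can occur. A patient removed after SBRT has already had the exposure, and what removal can stop is observation. If sites follow section 6.5 as written, ulcers, fistulas or bleeds arising later in that patient's first year may not reach the trial's toxicity data.

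Success on the primary endpoint means few observed events. Uncollected events therefore favour a conclusion of acceptable toxicity if the patient is counted without one. The interim toxicity rule would also trigger less often. Missing collection is harder to repair at analysis than a missing definition, so it is worth settling in the follow-up rule.

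**Working it through.** **1. Timing.** Section 6.1.4 delivers five fractions in one week, or over two. Section 13.1.1 starts the endpoint more than 3 months after SBRT, and section 13.4.2 judges it at one year. The calendar visits in that window are months 4, 6, 9 and 12. Anyone removed between the end of SBRT and month 12 leaves with part of the window unobserved.

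**2. Who has a toxicity route?**

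| Patient status | Follow-up named | Where |
|---|---|---|
| On study, attending | Calendar visits with AE evaluation | Section 10 |
| On study, cannot return | Telephone toxicity evaluation | Section 10, footnote 13 |
| On study, too ill to travel | Mailed questionnaires, local records | Section 6.4 |
| Past five years | Survival | Section 6.4 |
| Removed or discontinued | Survival | Section 6.5 |

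Section 6.4 uses the survival wording for patients whose scheduled visits have ended. That supports reading it in 6.5 as a reduced level of follow-up.

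**3. Reproduce the design (inputs from 13.4.2).** With event rate p,

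P(success) = Σ over x = 0 to 6 of P(Bin(16, p) = x) × P(Bin(44, p) ≤ 16 − x),

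and P(stop at stage 1) = P(Bin(16, p) ≥ 7).

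- p = 0.40: P(success) = 0.0209 (stated type I error 2%); P(stop) = 0.4728 (stated 0.47).
- p = 0.20: P(success) = 0.9076 (stated power 91%).

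The plan's figures are confirmed.

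**4. Illustration: missed events counted as event-free.** Assume a fraction f of events is missed. A true rate of 0.40 is then observed as 0.40 × (1 − f).

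| f (assumed) | Observed rate | Type I error | P(stop at stage 1) |
|---|---|---|---|
| 0 | 0.40 | 2.1% | 0.47 |
| 5% | 0.38 | 4.2% | 0.41 |
| 10% | 0.36 | 7.9% | 0.34 |

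**5. What those fractions mean in patients.** At 40%, 0.40 × 60 = 24 events are expected. Missing 5% is 1.2 events and missing 10% is 2.4. If removed patients carry average risk and all leave before their event, this needs 0.05 × 60 = 3 or 0.10 × 60 = 6 removals per cohort. If 5% or 10% of patients are removed but each loses only half of the event risk, the observed rate is 0.40 × (1 − f/2) = 0.39 or 0.38. Type I error is then 3.0% or 4.2%.

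**6. Dependence on classification.** Suppose instead that 3 or 6 patients are excluded, with stage 1 intact and removal unrelated to toxicity. Scaling the final cutoff gives 16 × 57/60 = 15.2, taken as 15, and 16 × 54/60 = 14.4, taken as 14. Type I error stays at 2.1% in both cases, and power is 0.8955 and 0.8812 against 0.9076. Leaving the cutoff at 16 gives 3.9% and 7.0%. So the size in step 4 depends on a rule that the plan does not state.

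**The case against.** The strongest reply is that section 6.5 never says survival alone. It can be read as a minimum that applies to everyone, with no instruction to stop recording toxicity. That is a fair reading of one sentence. But no section names toxicity follow-up after removal, and staff who follow the text would have no basis for continuing it.

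The second reply is that few patients are affected, and much of this stands. Progression is not a removal criterion. Section 6.4 leaves later antineoplastic treatment to the medical oncologist, so needing a disallowed treatment has little scope after SBRT. Patients who are ill but on study keep the telephone and records routes, and calendar footnote 4 accepts local evaluations. Failure to meet planning constraints (6.1.3) arises before treatment. Withdrawal of consent may bar collection whatever the protocol says.

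A reader might infer more than the documents support:

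- **That removed patients stay in the primary denominator as event-free.** Section 13.4.2 fixes the counts at 16 and 60 but does not classify removed patients. Section 11.1.1 makes patients evaluable for toxicity at the follow-up intervals, and no toxicity population is defined.
- **That their events are lost for good.** Section 7.2 keeps toxicities below grade 3 in patient charts, and section 11.1.7 plans a chart review at completion. Recovery could be incomplete, but total loss is not shown.
- **That they leave safety surveillance.** Section 7.2 requires reporting of all fatal events and of serious unanticipated events, with no stated exemption for removed patients.
- **That removal is linked to toxicity.** Some listed reasons make this plausible, but the documents give no evidence, and the calculation does not model it.

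**Conclusion.** The gap is real but limited. Section 6.5 names only survival follow-up after removal or discontinuation, and nothing elsewhere continues late-toxicity assessment through the one-year window. The correctable group is treated patients removed by the protocol director, or who stop visits without withdrawing consent to data collection.

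The size cannot be established from the documents. The figures of 4.2% and 7.9% type I error, and of 0.41 and 0.34 for stopping at stage 1, rest on two assumptions: that 5% or 10% of events are missed, and that the patients concerned are counted as event-free. The plan states neither. They show the direction and sensitivity of the rule and do not predict its behaviour in this trial. The undefined toxicity population is a related gap, which a change to 6.5 would not close. This point is a cheap improvement and does not show that the primary analysis is invalid.

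**What to change.** Replace the last sentence of section 6.5 with wording to this effect: any patient who received at least one SBRT fraction, and who is removed or stops visits without withdrawing consent to data collection, continues late GI toxicity follow-up at the calendar time points through month 12, by telephone and outside records as in calendar footnote 13 and section 6.4, in addition to survival follow-up. Survival-only follow-up applies to patients who decline toxicity data collection.

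Month 12 matches the one-year primary outcome. The change leaves treatment and the reasons for removal as they are. Its cost is one amended sentence and a few extra calls and record requests by existing staff.
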